6.8. Multiple Comparisons/Multiplicity

This study was designed to obtain preliminary estimates of safety and immune response to the A/H7N9 vaccination in healthy adults. The study was not designed to test any specific null hypothesis, and as such no adjustment for multiple comparisons will be performed.

7. STUDY SUBJECTS

7.1. Subject Disposition

Table 14 will present a summary of the reasons that subjects were screened but not enrolled.

The number and percentage of enrolled subjects excluded from each analysis population by treatment arm and age stratum, are presented in Table 15 and Table 16. A listing of subjects excluded from each analysis population will be presented in Listing 5.

The disposition of subjects in the study will be tabulated by treatment arm and age stratum (Table 17 and Table 18). The table will show the total number of subjects screened, randomized, receiving the first study vaccination, receiving the second study vaccination, completing the blood draw for the primary immunogenicity endpoints, and completing the last visit.

A flowchart showing the disposition of study subjects, adapted from the CONSORT Statement [4] will be included and will present the number of subjects screened, randomized, lost to follow up, and analyzed, by treatment arm (Figure 1).

A listing of subjects who were discontinued from treatment or terminated from study followup and the reason will be included in Listing 2.

7.2. Protocol Deviations

A summary of subject-specific protocol deviations will be presented by the deviation category and deviation type, treatment arm, and age stratum for all enrolled subjects (Table 9). Major deviations that will be reviewed for possible exclusion of immunogenicity results from the PP population include deviations related to eligibility/enrollment, treatment administration schedule, follow-up visit schedule, and receipt of exclusionary vaccines or medications. All subject-specific protocol deviations and non subject-specific protocol deviations will be included in Listing 3 and Listing 4.

8. IMMUNOGENICITY EVALUATION

Immunogenicity data summaries and analysis for primary and secondary endpoints will be presented for the mITT and PP populations. Immune responses in terms of strain-specific A/H7N9 HAI and Neut antibody titers will be summarized by treatment arm and age stratum at each time point. Descriptive summary statistics will be provided for all assays and time points including number of subjects with non-missing results, percentage of subjects with titers ≥1:40, percentage of subjects achieving seroconversion, and GMTs along with corresponding 95% CI. Exact confidence intervals will be presented for proportional endpoints. Summaries of primary and secondary immunogenicity endpoints are presented in Table 29, Table 30, Table 31, Table 32, Table 33, Table 34, Table 35, and Table 36.

RCD curves will be presented for post-vaccination HAI and Neut antibody titers. Plots for each assay will be generated with 4 panels (8 days post vaccination 1, 21 days post vaccination 1, 8 days post vaccination 2, 21 days post vaccination 2, and 180 days post vaccination 2), and separate curves within each panel for each treatment arm and age stratum, as shown in Figure 2, Figure 3, Figure 4, and Figure 5.

Figures depicting the HAI and Neut GMT over time will also be presented as shown in Figure 6, Figure 7, Figure 8, and Figure 9.

The spearman correlation between HAI, Neut, and Neuraminidase antibody titers will be calculated at each time point over all groups. The correlation will be depicted in scatter plots as Figure 10 and Figure 11.

Individual HAI and Neut assay results will be provided in Listing 8.

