11.6.3 Immunogenicity Data

Summaries and analysis of immunogenicity data will be presented for the mITT and PP populations.

Immune responses in terms of strain-specific 2017 H7N9 HAI and Neut antibody titers will be summarized by treatment arm at each time point. Analyses will include percentage of subjects with a titer ≥1:40, percentage of subjects achieving seroconversion (defined as either a prevaccination titer <10 and a post-vaccination titer ≥1:40 or a pre-vaccination titer ≥1:10 and a minimum four-fold rise in post-vaccination antibody titer), and GMTs along with corresponding 95% confidence intervals. Descriptive summary statistics will be provided for all assays and time points. The correlation between HAI and Neut antibody titers will be evaluated. Plots such as reverse cumulative distributions or longitudinal presentations of GMTs will be presented.

Additionally, the immune response, as described above, will be summarized by available covariates, such as age, sex, body mass index, and prior receipt of seasonal influenza vaccine(s), and these covariates may be considered statistical modeling. As an exploratory analysis, models will be developed to evaluate the relationship between dosage and adjuvant on immune response. For example, logistic regression may be used to examine the relationship of proportion of responders with dosage and adjuvant, and available covariates may be considered for inclusion in the model.

Additionally, N9 NA specific antibody assays are in development. If successful, N9 NA specific responses may be assessed at baseline, and 8, 29, 43 and 202 after receipt of the first study vaccination. For each time point summaries will include percentage of subjects with detectable N9 NA response (to be defined in SAP based following assay development and selection) and GMTs along with corresponding 95% confidence intervals. Descriptive summary statistics will be provided for all assays and time points. The correlation of N9 NA response with HAI and Neut antibody titers will be evaluated, and plots such as reverse cumulative distributions or longitudinal presentations of GMTs will be presented.

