4.4.3. Method of Assigning Subjects to Treatment Groups (Randomization)

Enrollment/randomization will be performed through the enrollment module in the electronic data capture system maintained by the Statistical and Data Coordinating Center (SDCC).

Eligible subjects will be stratified by clinical site and age (19-64 years, ≥65 years) then randomly assigned with allocation (2:2:2:1:1) to one of 5 treatment arms indicated in Table 1. The treatment sequence was generated using permuted block randomization to provide an approximately balanced allocation to the treatment arms during the study.

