5. SAMPLE SIZE CONSIDERATIONS

This study is planned to enroll a minimum of 160 subjects in each adjuvanted treatment arm (100 in 19-64 years age stratum, 60 in ≥65 years stratum), and 80 subjects in each unadjuvanted treatment arm (50 in 19-64 years age stratum, 30 in ≥65 years stratum). The sample size for this study was selected to obtain preliminary estimates in a time critical manner. While this study is not designed to test any specific null hypothesis, the following tables illustrate the precision and power that is available for select estimates and comparisons of interest.

Table 4 indicates the probability of observing one or more safety events, such as solicited injection site or systemic reactogenicity events or an unsolicited non-serious AE of a particular type for a single adjuvanted treatment arm/stratum (N = 60, or 100), for a single adjuvanted treatment arm combined over age strata (N=160), for all subjects receiving unadjuvanted vaccine (N = 160), and for all subjects receiving adjuvanted vaccine (N = 480).

Binomial confidence intervals (CI) are widest (have the least precision) when the response rate is 50%. Table 5 is presented to indicate the worst case scenario for precision of observed exact (Clopper-Pearson) binomial confidence intervals.

Table 6 illustrates the minimum detectable differences in the proportion of subjects responding (e.g., attaining seroconversion or a titer $\ge 1:40$) between two adjuvanted treatment arms within each stratum using a two-sided Likelihood Ratio Test and alpha = 0.05.

Over enrollment is allowed, to ensure a minimum of n=100 per adjuvanted treatment arm in the 19-64 years age stratum, therefore power calculations for this stratum assume n=100 per group. Based on previous DMID A/H7N9 trials it is expected 5% of enrolled subjects in this stratum may be excluded from analysis of the primary endpoint. In the event that only 100 subjects are actually enrolled in a treatment arm, the small dropout rates anticipated would have a minimal impact on the calculations presented in Table 7.

Within the ≥65 years treatment arm a dropout rate of up to 12% is expected based on previous DMID trials in this population, so a minimum of 60 subjects are planned to enroll in each adjuvanted treatment arm to ensure at least 50 are available for analysis of the primary immunogenicity endpoint.

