- Figure 8: Geometric Mean Titers of Neutralizing Antibody against A/H5N8 Study Day, Treatment Arm and Age Stratum, Modified Intent to Treat Population*
- Figure 9: Geometric Mean Titers of Neutralizing Antibody against A/H5N8 by Study Day, Treatment Arm and Age Stratum, Per Protocol Population*

Figure 10: Correlation of Hemagglutination Inhibition Antibody and Neutralizing Antibody Against 2017 A/H7N9 by Study Day, Treatment Arm and Age Stratum, Modified Intent-to-Treat Population*

[Implementation Note: A generic sample figure is shown below. The scatter plots should be presented in a single figure with separate panels for each visit (Baseline, D8, D22, D29, D43, D202. Visit labels should be included in the panel header. Within each panel distinct marker types and colors should be used to indicate the treatment arms, with treatment group labels included in a legend.). Each treatment arm should have a unique color and marker shape, with open/closed markers used to distinguish strata within treatment arm $(19-65, \ge 65)$ The spearman correlation should be calculated over all subjects and annotated within each panel as "Spearman Correlation (r=0.xx, p=0.xx)"]

[figure not shown]

Figure with Similar format:

Figure 11: Correlation of Hemagglutination Inhibition Antibody and Neutralizing Antibody Against 2017 A/H7N9 by Study Day, Treatment Arm and Age Stratum, Per Protocol Population*

Figure 12: Reverse Cumulative Distribution of Hemagglutination Inhibition Antibody against [Antigenically Drifted Strain] by Study Day, Treatment Arm and Age Stratum, Per Protocol Population*

[Implementation Note: A generic sample figure is shown below. The RCD curves should be presented in a single figure with separate panels for each study day (Baseline[Day1], Day 8, Day 22, Day 29, Day 43, Day 202. Visit labels should be included in the panel headers. Within each panel individual curves should be used for each treatment arm and strata within treatment arm (ten curves). Each treatment arm should have a separate color with dashed/solid lines used to distinguish strata (19-65, ≥65)]

[Implementation Note: repeat for all heterologous strains]

[figure not shown]

Figure with Similar Format:

Figure 13: Reverse Cumulative Distribution of Neutralizing Antibody against [Antigenically Drifted Strain] by Study Day, Treatment Arm and Age Stratum, Per Protocol Population

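### The one Spearman coefficient per visit is pooled over all arms, so after vaccination it includes the AS03 shift and cannot by itself show association within an arm

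*SAP*

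**What the plan says.** SAP section 8 states: "The spearman correlation between HAI, Neut, and Neuraminidase antibody titers will be calculated at each time point over all groups". The implementation note for Figure 10 (SAP 14.2.2) repeats the rule: "The spearman correlation should be calculated over all subjects and annotated within each panel", with r and p both printed. Figure 11 has the same format. The Figure 16 note gives the same instruction for the drifted strains, and Figures 17 and 18 follow its format.

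The titles of these figures name treatment arm and age stratum, but both appear only through plotting symbols. The note asks that "distinct marker types and colors should be used to indicate the treatment arms", with open and closed markers for the age strata. Neither document plans a within-arm, stratified or partial coefficient.

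Protocol 11.6.3 leaves the handling of arms open: "The correlation between HAI and Neut antibody titers will be evaluated". It says the same for N9 NA responses against HAI and Neut titers. The SAP defers the NA analyses to an addendum (sections 4.5.2 and 8.3.4).

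**The concern.** The trial is designed around a large difference between arms. Protocol 2.2 expects the adjuvanted vaccine to be more immunogenic. The sample-size sections (Protocol 11.4.3, SAP 5) illustrate 0.10 responders without adjuvant against 0.50 to 0.90 with it. If AS03 raises both titers, most adjuvanted subjects rank high on both axes and most unadjuvanted subjects rank low on both. That alone produces a positive rank correlation over all subjects, even if one assay says nothing about the other among people given the same product.

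The printed p-value tests independence in the pooled sample, which the adjuvant effect already breaks. A reader of a post-vaccination panel cannot tell how much of r comes from the vaccine and how much from association between subjects in the same arm. The drifted-strain figures have the same feature. The NA correlations would share it if the addendum keeps the rule in section 8.

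**Working it through.** **Plan's own figures.** The documents state no correlation, so there is none to reproduce. As a check on the inputs, the Farrington-Manning lower bounds for 0.10 against 0.50, 0.60, 0.70, 0.80 and 0.90 were recomputed:

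- N = 100 and 50: 0.256, 0.356, 0.458, 0.563, 0.672 (Protocol Table 6: 0.26, 0.36, 0.46, 0.56, 0.67).
- N = 50 and 25: 0.187, 0.286, 0.388, 0.493, 0.604 (Protocol Table 7: 0.19, 0.29, 0.39, 0.49, 0.60).

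**Inputs from the documents**

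- Allocation 2:2:2:1:1 (SAP 4.4.3). With 160 per adjuvanted and 80 per unadjuvanted arm (SAP 5), N = 3×160 + 2×80 = 640, and the adjuvanted share is w = 480/640 = 0.75.
- Responder rates pU = 0.10 and pA = 0.50 to 0.90 (SAP 5).
- Titers reported as 10×2^k, with values below 10 set to 5 (SAP 4.5.2).

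**Assumptions not in the documents.** Neut has the HAI responder rates. The three adjuvanted arms respond alike, as do the two unadjuvanted arms. There is no age effect. Log2 titers are normal with SD 1.0, 1.5 or 2.0.

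**Step 1, by formula.** Take titer ≥1:40 (yes/no) on each assay, independent within every arm. The pooled covariance is then w(1−w)(pA−pU)², and each variance is p̄(1−p̄) with p̄ = w·pA + (1−w)·pU. Hence

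phi = w(1−w)(pA−pU)² / [p̄(1−p̄)].

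- pA = 0.50: p̄ = 0.40; 0.1875×0.16/0.24 = 0.125
- pA = 0.70: p̄ = 0.55; 0.1875×0.36/0.2475 = 0.273
- pA = 0.90: p̄ = 0.70; 0.1875×0.64/0.21 = 0.571

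The true within-arm value is zero in all three cases.

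**Step 2, by simulation on the titer scale** (400 trials per setting, N = 640). The pooled Spearman is set against the five within-arm values averaged on Fisher's z scale with weights n−3. Ranges cover SD 1 to 2.

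| Latent within-arm correlation | Pooled, pA 0.50 | Pooled, pA 0.70 | Pooled, pA 0.90 | Arm-stratified |
|---|---|---|---|---|
| 0 | 0.20–0.22 | about 0.35 | 0.48 | about 0.00 |
| 0.5 | 0.57–0.58 | 0.64–0.65 | 0.72–0.73 | about 0.45 |
| 0.8 | 0.78–0.80 | 0.82–0.85 | 0.86–0.88 | 0.72–0.75 |

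With zero within-arm correlation, the pooled p-value is below 0.05 in 99.8 to 100% of trials; the arm-stratified test rejects in 4 to 7%. The excess of pooled over stratified shrinks as the true correlation rises, to about 0.06 to 0.13 at latent 0.8.

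**Step 3, no arm effect.** With 0.10 responders in all arms and zero within-arm correlation, pooled r is 0.00 and p<0.05 in about 5% of trials. The inflation in step 2 therefore comes from the arm shift. Before vaccination there is no such shift.

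**Step 4, precision of the alternative.** The approximate Fisher-z standard error is 1/√(3×157 + 2×77) = 1/√625 = 0.040 for the arm-stratified value and 1/√637 = 0.040 for the pooled one. For single arms it is 1/√157 = 0.080 (adjuvanted) and 1/√77 = 0.114 (unadjuvanted). At 10% responders about 23 to 61% of unadjuvanted titers sit at the floor of 5. With latent correlation 0.5, the unadjuvanted within-arm Spearman is then 0.38 to 0.44.

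**The case against.** A pooled coefficient over the full titer range is a legitimate description, and section 8 says openly what it is. Marker colors and shapes let a reader see clustering by arm, so the figure titles are accurate as descriptions of the display. Listing 8 gives individual titers by arm, so within-arm values could be derived later. All of this stands. It is why the pooled value can stay if labelled. It does not supply the missing number, and the printed p-value still invites a reading that the pooled sample cannot bear.

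A reader might infer that the trial relies on this figure to judge how far the assays rank individuals alike, and so overstates their agreement. The documents do not support that. No HAI-Neut correlation appears among the objectives or outcome measures, Protocol 11.6.3 gives no interpretation, and the SAP never calls the coefficient agreement. The one correlation among the outcome measures (Protocol 3.2.3) relates vaccine NA content to NA antibody, which is a different quantity. A reader might also infer that the assays disagree within arms; nothing in the documents or in this calculation shows that.

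It is also fair that per-arm values multiply. Five arms by five post-vaccination panels give 25 coefficients per figure and population, with no multiplicity adjustment (SAP 6.8). The arm-stratified value should therefore be the main one.

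**Conclusion.** The point holds as a limit on what the post-vaccination r and p can show. They mix the shift between arms with association inside arms and cannot separate the two. Under the plan's illustrative rates, the shift alone yields a pooled r of about 0.2 to 0.5, nearly always with p<0.05. If the assays are already strongly associated within arms, the excess is modest.

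The size rests on equal HAI and Neut responder rates, which the plan does not state: SAP 5 introduces those rates for HAI. It also rests on equal response among the adjuvanted arms and between the two unadjuvanted arms. The assumed SD matters little: going from 1 to 2 moves the pooled value by no more than about 0.03. An age effect in the same direction on both assays would be pooled as well and would add to the excess.

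The point does not extend to every visit. Day 1 has no arm effect, SAP 8.3.1 expects little or no baseline antibody, and Day 8 may be little affected if responses are still low. Nor does it show a settled fault in the NA analysis, whose plan is still to be written. No primary or secondary endpoint, regression model or halting rule depends on this coefficient.

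**What to change.** For the post-vaccination panels of Figures 10-11 and 16-18:

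- Add Spearman's coefficient within each treatment arm.
- Add one arm-stratified value and make it the main annotation. Use either the Fisher-z average of the within-arm coefficients with weights n−3, or a Spearman partial correlation on arm and age stratum. Name the choice in SAP section 8.
- Keep the pooled r only with a label saying that it includes differences between arms.
- Write the same rule into the NA addendum.

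Protocol 11.6.3 leaves the handling of arms open, so no protocol change is needed. The cost is a by-arm run, a short averaging step and extra annotation. The arm-stratified value loses almost no precision. Single-arm values are less precise, and ties at the floor titer of 5 attenuate them in the unadjuvanted arms, which a footnote should say.

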8.1. Primary Immunogenicity Analysis

The primary immunogenicity endpoints HAI and Neut seroconversion, percentage of subjects with titer ≥1:40, and GMTs against the homologous A/H7N9 vaccine strain 21 days after the second vaccination will be summarized as described above. Regression modelling of seroconversion and log titers is planned as described in Section 8.3.2.

8.2. Secondary Immunogenicity Analyses

The primary immunogenicity endpoints HAI and Neut seroconversion, percentage of subjects with titer ≥40, and GMTs against the homologous A/H7N9 vaccine strain 8 and 21 days after the first vaccination and 8 days after the second vaccination will be summarized as described above. No formal hypothesis testing is planned.

8.3. Exploratory Immunogenicity Analyses

Immunogenicity data summaries and analysis for exploratory endpoints will be presented for the PP populations.

8.3.1. Covariate Analysis

As an exploratory analysis, seroconversion and GMT of serum antibody for both HAI and Neut at 21 and 180 days after second vaccination will be summarized by treatment arm stratified by age (categorized as those subjects ages 19-34, 34-49, 50-64, 65-80, and ≥81

years) (Table 37, Table 38, Table 39, and Table 40), by sex (Table 41, Table 42, Table 43, and Table 44), by BMI (Table 45, Table 46, Table 47, and Table 48), and by prior receipt of seasonal influenza vaccines (Table 49, Table 50, Table 51, and Table 52). These stratified summaries will be presented for the PP population. It is anticipated that subjects will have little to no pre-existing antibody at baseline, so seroconversion and titer ≥ 40 endpoints will be similar.

8.3.2. Regression Modeling

Logistic and multivariate linear regression will be utilized to test for the effects of the HA antigen dose and the AS03 adjuvant on seroconversion and GMT, respectively, for the PP population. Similar models will be fit for HAI and Neut Antibodies. Separate models will be fit for data from Day 21 post dose 2 and Day 180 post dose 2.

Logistic regression will be fit to examine the relationship of HAI seroconversion at 21 days after the 2nd study vaccination with treatment group and age strata (19-64 years, ≥65 years). If the available titer data meets the required assumptions of normality after log transformation, multiple linear regression will be fit to examine the relationship of log transformed titers at 21 days after the 2nd study vaccination with treatment arm and age strata (19-64 years, ≥65 years). Both models will be fit with and without adjustment for the following covariates (*Z*): sex (female, male), BMI (<30, ≥30), and prior receipt of seasonal influenza vaccine (none in past 2 seasons, at least once in past 2 seasons). Modeling assumptions will be checked using standard diagnostic methods (e.g., using the INFLUENCE option in PROC LOGISTIC or PROC GLM). Parameter estimates and odds ratio estimates for the logistic models will be presented in Table 53, Table 54, Table 55, Table 56, Table 57, Table 58, Table 59, and Table 60. Parameter estimates for the multiple linear regression models will be presented in Table 61, Table 62, Table 63, Table 64, Table 65, Table 66, Table 67, and Table 68.

Model 1A: Logistic Regression (without covariate adjustment):

 $logit[P(seroconversion)] = \beta_0 + \beta_1 \times Treatment + \beta_2 (Age \ge 65) + \varepsilon$

Model 1B: Logistic Regression (with covariate adjustment):

$$logit[P(seroconversion)] = \beta_0 + \beta_1 \times Treatment + \beta_2 (Age \ge 65) + \beta_3 \times Z + \varepsilon$$

Model 2A: Multiple Linear Regression (without covariate adjustment):

$$log(titer) = \beta_0 + \beta_1 \times Treatment + \beta_2(Age \ge 65) + \varepsilon$$

Model 2B: Multiple Linear Regression (with covariate adjustment):

$$log(titer) = \beta_0 + \beta_1 \times Treatment + \beta_2(Age \ge 65) + \beta_3 \times Z + \varepsilon$$

Subjects missing data for one or more covariates will be excluded from Models 1B and 2B.

Models 1B and 2B, defined above, will also be fit for HAI at Day 21 replacing the binary age strata variable with age in years (continuous). The models as shown below assume a linear relationship between age in years and both probability of seroconversion and GMT. The validity of this assumption will be assessed prior to analysis and, if the relationship between age and response is found to be non-linear, adjustments will be made to model parameters to

satisfy regression assumptions. The results of these models will be presented in Table 69 and Table 70.

Model 3: Logistic Regression (with covariate adjustment):

$$logit[P(seroconversion)] = \beta_0 + \beta_1 \times Treatment + \beta_2 (Age in Years) + \beta_3 \times Z + \varepsilon$$

Model 4: Multiple Linear Regression (with covariate adjustment):

$$log(titer) = \beta_0 + \beta_1 \times Treatment + \beta_2(Age\ in\ Years) + \beta_3 \times Z + \varepsilon$$

Subjects missing data for one or more covariates will be excluded from Models 3 and 4.

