The goal of this clinical trial is to assess the safety, reactogenicity and immunogenicity of two doses of the 2017 H7N9 IIV administered with or without AS03 in healthy adult and the elderly individuals. The 2017 H7N9 IIV manufactured by Sanofi will be mixed at the site with or without AS03 and will be administered IM at different dosages with AS03 [3.75, 7.5 and 15 mcg HA per dose (based on label content)] or without AS03 (15 or 45 mcg HA per dose) to evaluate the dose-sparing potential of the adjuvant. Data from phase I clinical trials of avian IIVs suggest that they are poorly immunogenic and require multiple high-doses or the inclusion of an adjuvant to induce serum HAI titer of 40 or greater against the study vaccine virus. In previous NIAID sponsored clinical trials of 2013 H7N9 IIV, 2 doses of non-adjuvanted 45 mcg of HA per dose did not confer significant seroprotection [46, 48]. However, to confirm the poor immunogenicity of the 2017 H7N9 IIV, a study arm with 2 high-doses (45 mcg HA per dose administered approximately 21 days apart) of non-adjuvanted 2017 H7N9 IIV is included in the study design. The 45 mcg dosage represents a 12-, 6-, and 3-fold excess of vaccine antigen, respectively, over the 3.75 mcg, 7.5 mcg, and 15 mcg dose-sparing formulations achievable with the AS03 adjuvant. In addition to assessing antigen-sparing strategies, another goal of this study is to assess in at least a subset of samples, if serum IgG elicited by the 2017 H7N9 IIV recognize antigenically drifted variants of influenza A/H7 viruses. Since antibodies targeting the NA may represent an independent correlate of protection against influenza infection [11-13], we plan to assess the NA content of the 2017 H7N9 vaccine and determine if there is a dose-specific correlation of NA content with elicited humoral antibody responses to the N9 NA.

Based on previously conducted studies with a 2013 H7N9 IIV manufactured by Sanofi Pasteur administered with or without AS03, we anticipate that two doses of the 2017 H7N9 IIV

administered IM at different dosages with AS03 adjuvant approximately 21 days apart will be well-tolerated and more immunogenic compared to the non-adjuvanted vaccine in healthy adult and elderly individuals.

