4.4.4. Selection of Doses in the Study

Participants in this study are to receive two A/H7N9 vaccinations at HA doses of 3.75, 7.5, or 15 mcg with AS03 adjuvant, or at HA doses of 15 or 45 mcg without adjuvant. The 3.75, 7.5, or 15 mcg with AS03 doses are selected to evaluate safety and immunogenicity of antigen sparing dose strategies. Per FDA Guidance [5], the 15 mcg non-adjuvanted dose was selected to compare immune response with the 15 mcg adjuvanted vaccine. The 45 mcg non-adjuvanted dose is included to confirm the expected poor immunogenicity of non-adjuvanted vaccine at a high dose.

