Per FDA guidance [5,6], for differences in HAI antibody response rates, the lower confidence limit on the appropriate point estimate excluding equality (i.e., 0 for the difference parameter) may be sufficient to demonstrate the added value of the adjuvant. Table 8 and Table 9 show the lower bound of the 95% confidence interval for the difference in the proportion of responders between the adjuvanted and unadjuvanted arms (e.g., 15 mcg + AS03 minus 45 mcg unadjuvanted) assuming the proportion of responders in the unadjuvanted arm is 0.10 and considering a range for the proportion of responders in the adjuvanted arm ranges from 0.50 to 0.90.

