- Table 52: Summary of Neutralizing Antibody Against 2017 A/H7N9 by Treatment Arm, Age Stratum and Prior Seasonal Influenza Vaccination at 180 Days Post Second Vaccination, Per-Protocol Population*

Table 53: Logistic Regression Model to Evaluate the Relationship of HA Antigen Dose and AS03 Adjuvant with HAI Seroconversion Against 2017 A/H7N9 at 21 Days Post Second Study Vaccination, Per Protocol Population*

Model Parameter	Parameter Levels	Parameter Estimate	SE	p-value	Odds Ratio	95%CI
Treatment	3.75 mcg with AS03 Adjuvant (reference)	-	-	-	-	-
	7.5 mcg with AS03 Adjuvant	XXX.X	xxx.x	x.xxx	xx.x	xx.x-xx.x
	15 mcg with AS03 Adjuvant	xxx.x	xxx.x	x.xxx	xx.x	xx.x-xx.x
	15 mcg without AS03 Adjuvant	xxx.x	xxx.x	x.xxx	xx.x	xx.x-xx.x
	45 mcg without AS03 Adjuvant	xxx.x	xxx.x	x.xxx	xx.x	xx.x-xx.x
Age	19-64 years (reference)	-	-	-	-	-
	≥65 years	XXX.X	xxx.x	x.xxx	xx.x	xx.x-xx.x
Interaction: Age*Treatment	Age*3.75 mcg with AS03 Adjuvant	-	-	-	-	-
	Age*7.5 mcg with AS03 Adjuvant	XXX.X	xxx.x	x.xxx	xx.x	xx.x-xx.x
	Age*15 mcg with AS03 Adjuvant	XXX.X	xxx.x	x.xxx	xx.x	xx.x-xx.x
	Age*15 mcg without AS03 Adjuvant	XXX.X	xxx.x	x.xxx	xx.x	xx.x-xx.x
	Age*45 mcg without AS03 Adjuvant	XXX.X	xxx.x	X.XXX	xx.x	xx.x-xx.x
	Age*3.75 mcg with AS03 adjuvant	-	-	-	-	-

N = XX subjects with results available at 21 days post second vaccination in the per protocol population. XX subjects missing covariate data were excluded from this analysis.

P-value for Treatment = 0.XXX; P-value for Age = 0.XXX; P-value for interaction of Treatment and Age = 0.XXX.

- Table 54: Logistic Regression Model to Evaluate the Relationship of HA Antigen Dose and AS03 Adjuvant with Neut Seroconversion Against 2017 A/H7N9 at 21 Days Post Second Study Vaccination, Per Protocol Population*
- Table 55: Logistic Regression Model to Evaluate the Relationship of HA Antigen Dose and AS03 Adjuvant with HAI Seroconversion Against 2017 A/H7N9 at 180 Days Post Second Study Vaccination, Per Protocol Population*
- Table 56: Logistic Regression Model to Evaluate the Relationship of HA Antigen Dose and AS03 Adjuvant with Neut Seroconversion Against 2017 A/H7N9 at 180 Days Post Second Study Vaccination, Per Protocol Population*

Table 57: Logistic Regression Model to Evaluate the Relationship of HA Antigen Dose and AS03 Adjuvant with HAI Seroconversion Against 2017 A/H7N9 at 21 Days Post Second Study Vaccination, Adjusted for Baseline Covariates, Per Protocol Population*

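### No planned table reports the comparison Group 4 was chosen for (15 mcg + AS03 against 15 mcg alone), or any adjuvanted-minus-unadjuvanted responder difference with a confidence interval

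*SAP*

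**What the plan says.** **Purpose of the arm.** SAP 4.4.4 says "the 15 mcg non-adjuvanted dose was selected to compare immune response with the 15 mcg adjuvanted vaccine".

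**Aim of the models.** SAP 8.3.2 states that "Logistic and multivariate linear regression will be utilized to test for the effects of the HA antigen dose and the AS03 adjuvant". The outcomes modelled are seroconversion and log titer, in the per-protocol population. SAP 8.1 refers the primary immunogenicity analysis to that section. Protocol 11.6.3 describes the modelling as exploratory: "models will be developed to evaluate the relationship between dosage and adjuvant on immune response".

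**Precision.** SAP 5 says that, for HAI response rates, a lower confidence limit for the difference that excludes 0 "may be sufficient to demonstrate the added value of the adjuvant". Its example is "15 mcg + AS03 minus 45 mcg unadjuvanted". SAP Tables 7 and 8 (Protocol Tables 6 and 7) give Farrington-Manning lower limits for such a difference.

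**Planned output.** Tables 29-36, the subgroup Tables 37-52 and the drifted-strain Tables 71-72 give estimates and intervals within each arm. In the model shells (Tables 53-70) the first treatment row is "3.75 mcg with AS03 Adjuvant (reference") and the other four arms are compared with it. The footnotes add overall p-values, including "P-value for interaction of Treatment and Age".

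**The concern.** Group 3 against Group 4 is the only pair of arms with the same antigen dose and different adjuvant status, so it is the only pair that isolates AS03. In Tables 53-70 the two unadjuvanted rows compare 15 or 45 mcg alone with 3.75 mcg + AS03, which changes dose and adjuvant at once. The difference in responders that SAP 5 uses to describe precision has no output table, either for Group 3 minus Group 4 or for the SAP's own example, Group 3 minus Group 5.

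If the plan is followed exactly, the report gives no effect size with an interval for AS03 at equal dose. A reader would have to compare two per-arm intervals by eye, which is a more conservative check than the interval for the difference. The contrast and the interval method would also be left to be chosen after unblinding.

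**Working it through.** **1. Can the equal-dose contrast be read from a model table?** Let b3 and b4 be the printed coefficients of Groups 3 and 4 against Group 1, and g3 and g4 their Age*Treatment coefficients.

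- Ages 19-64: the contrast is b3 - b4.
- Ages ≥65: the contrast is (b3 + g3) - (b4 + g4).
- Variance at 19-64: Var(b3) + Var(b4) - 2 Cov(b3, b4).

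The point estimate follows by subtraction. Its interval needs a covariance that no shell prints. With the interaction in the model, the treatment rows of the age-stratum tables (53-68) describe ages 19-64 only, and no row gives a between-arm contrast for ages ≥65 directly. The equations in SAP 8.3.2 contain no interaction term, so the text and the shells disagree about which model is fitted.

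**2. Reproducing the plan's precision figures.** The Farrington-Manning lower limit is the value d that solves

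(p1 - p2 - d) / sqrt[ q1(1 - q1)/n1 + q2(1 - q2)/n2 ] = 1.96,

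where q1 and q2 are the maximum-likelihood rates restricted to q1 - q2 = d. For 0.50 against 0.10 with 100 and 50 subjects, d = 0.256 gives q1 = 0.434 and q2 = 0.178. The standard error is 0.0734, and (0.40 - 0.256)/0.0734 = 1.96.

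| Adjuvanted rate (unadjuvanted 0.10) | 0.50 | 0.60 | 0.70 | 0.80 | 0.90 |
|---|---|---|---|---|---|
| 100 vs 50, computed | 0.256 | 0.356 | 0.458 | 0.563 | 0.672 |
| 100 vs 50, SAP Table 7 | 0.26 | 0.36 | 0.46 | 0.56 | 0.67 |
| 50 vs 25, computed | 0.187 | 0.286 | 0.388 | 0.493 | 0.604 |
| 50 vs 25, SAP Table 8 | 0.19 | 0.29 | 0.39 | 0.49 | 0.60 |

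All ten figures agree after rounding.

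**3. Do the planned per-arm intervals convey the same thing?** The analysed numbers are those in SAP Tables 7 and 8. The responder counts are illustrative assumptions, with 50% responding on AS03. The per-arm intervals are exact (Clopper-Pearson).

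| AS03 arm (exact 95% CI) | Unadjuvanted arm (exact 95% CI) | Overlap? | Lower limit of difference |
|---|---|---|---|
| 25/50 (0.355-0.645) | 3/25 (0.025-0.312) | no | 0.162 |
| 25/50 | 4/25 (0.045-0.361) | yes | 0.114 |
| 25/50 | 5/25 (0.068-0.407) | yes | 0.068 |
| 25/50 | 6/25 (0.094-0.451) | yes | 0.024 |
| 25/50 | 7/25 (0.121-0.494) | yes | -0.018 |
| 50/100 (0.398-0.602) | 12/50 (0.131-0.382) | no | 0.096 |
| 50/100 | 13/50 (0.146-0.403) | yes | 0.075 |
| 50/100 | 16/50 (0.195-0.467) | yes | 0.012 |
| 50/100 | 17/50 (0.212-0.488) | yes | -0.009 |

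The two readings therefore disagree at 4 to 6 of 25 (16-24%) and at 13 to 16 of 50 (26-32%). With 60% responding on AS03, the disagreement moves to 7 to 9 of 25 (28-36%) and 18 to 21 of 50 (36-42%). With 70%, it moves to 9 to 11 of 25 (36-44%) and 23 to 26 of 50 (46-52%). At the SAP's 10% rate, 5/50 has an exact interval of 0.033-0.218, well clear of 0.398.

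**The case against.** The strongest reply is that the trial is descriptive and loses nothing. Protocol 11.2 and SAP 6.8 say it was not designed to test a specific hypothesis, and every endpoint is a per-arm percentage or GMT that the tables do report. That stands, and it limits this to a point about reporting.

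A reader might infer that the missing interval cannot be obtained. The documents do not support that. Tables 33-36 give n and whole-number percentages by arm and stratum, which fix the count for any denominator up to 100, so the unadjusted difference and odds ratio follow. For the adjusted models, Listing 8 (titers), Listing 6 (age, sex, BMI, prior vaccination) and Listing 5 (exclusions) let a holder of the study report refit them.

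A reader might also infer that the plan prints the dose contrasts and neglects the adjuvant. It prints only contrasts with 3.75 mcg + AS03. Neither 7.5 against 15 mcg with AS03 nor 15 against 45 mcg alone is shown. This is ordinary reference coding. The chosen reference suits the aim in Protocol 2.2 "to evaluate the dose-sparing potential of the adjuvant", because it sets the lowest adjuvanted dose against the unadjuvanted ones.

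A third tempting reading is that SAP 5 sets a success criterion which the analysis then fails to evaluate. The sentence sits under sample size, is worded as a possibility, and introduces tables offered as illustrations.

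Finally, the 50% adjuvanted rate used in the overlap examples is the bottom of the SAP's 50-90% range. At higher rates, disagreement needs unadjuvanted responses still further above the assumed 10%, and the documents expect poor unadjuvanted immunogenicity even at 45 mcg.

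What remains is that an estimation trial should print the estimate one of its arms was selected to provide.

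**Conclusion.** The gap is real and minor. No planned table gives Group 3 against Group 4, or any adjuvanted-minus-unadjuvanted responder difference with a confidence interval, although SAP 4.4.4 names the first as the reason for Group 4 and SAP 5 uses the second to describe precision. No data are lost and no planned estimate is wrong.

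In practice, per-arm intervals would mislead only if unadjuvanted response is well above the SAP's 10%: from about 16% (ages ≥65) or 26% (ages 19-64) with 50% responding on AS03, and higher if AS03 does better. These thresholds assume the analysed numbers in SAP Tables 7 and 8. The documents give no separate expected rate for Group 4. Below the thresholds the direction of the result would be clear from the per-arm tables, but its size would still be reported without an interval.

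**What to change.** 1. Add one Day 43 table by age stratum, for HAI and Neut in the per-protocol population. It should show the difference in seroconversion with a Farrington-Manning 95% CI for Group 3 minus Group 4 and Group 3 minus Group 5, labelled descriptive and without multiplicity adjustment. That is 2 differences x 2 assays x 2 strata = 8 intervals.
2. Keep 3.75 mcg + AS03 as the reference. Add a Group 3 against Group 4 contrast by age stratum (odds ratio or GMT ratio with 95% CI) to the Day 43 age-stratum model tables 53, 54, 57, 58, 61, 62, 65 and 66. That is 8 tables x 2 strata = 16 contrasts.
3. Reconcile the equations in SAP 8.3.2 with the Age*Treatment term in the shells, since the by-stratum contrasts depend on it.

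**Cost.** One table shell, a few contrast statements and a short edit to SAP 8.3.2, with no new data. The report gains 8 + 16 = 24 unadjusted descriptive intervals. The odds ratio is undefined if Group 4 has no responders in a stratum. For 25 subjects the chance is 0.90^25 = 7% at a 10% response rate and 0.95^25 = 28% at 5%. For 50 subjects it is 0.90^50, under 1%, and 0.95^50 = 8%. The difference table still works then: 25/50 against 0/25 gives a lower limit of 0.35.
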